- Process of care/adherence variables:

Time from:

- Hospital admission to ICU/HDU admission
- Hospital admission to first diagnosis of suspected sepsis or suspected septic shock
- Randomisation to first research blood sample taken
- First blood sample taken to first blood sample delivered to laboratory

Analysis

Outcome definitions

The primary outcomes of the trial are (i) total duration of antibiotic treatment to 28 days following randomisation (superiority) measured in days as primary clinical effectiveness outcome, and (ii) 28-day all-cause mortality (non-inferiority) following randomisation as primary safety outcome. For the clinical effectiveness outcome, the use of antibiotics data will be recorded to the point where the participant stopped antibiotics. The use of antibiotics will also be recorded if participants either restarts antibiotics in hospital or discharged from hospital and the re-admitted and receives systemic antibiotics or discharged with antibiotics provided that these events are within 28 days following randomisation. The duration of antibiotics use will be calculated for each participant as the sum of the duration of each course of antibiotics administered from randomisation to day 28. For the safety outcome, all-cause mortality status on day 28 following randomisation will be recorded.

The Secondary effectiveness and safety outcome measures to 28 days following randomisation are

- Antibiotic duration and dose for the initial sepsis episode (duration in days from randomisation and dose measured as Defined Daily Dose)
- Antibiotic dose (measured as Defined Daily Dose)
- Unscheduled care escalation/re-admission
- Infection relapse/recurrence requiring further antibiotic treatment
- Super-infection defined as new infection at a different anatomical site
- Suspected antibiotic adverse reactions
- Time to 'fit' for hospital discharge

The 90-days all-cause mortality will also be analysed as secondary outcome using linked data, for example, from NHS Digital and the Intensive Care National Audit and Research Centre.

Analysis methods

Participants' baseline characteristics and outcomes will be summarised mean and standard deviation if data are continuous or frequency and percentage if data are categorical. The median and interquartile range will be presented if data are non-normal.

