The primary effectiveness analyses will assess whether any of the biomarker interventions are better than standard care. The primary analysis approach for the duration of antibiotics will be intention-to-treat (ITT). ITT analysis will consist of all randomised patients and will assess the effect of treatment assignment. For the ITT analysis, linear mixed effects regression models will be fitted to estimate the treatment effect having adjusted for age, gender and the stratification variables (sepsis severity, recruiting centre (random effect) and surgery within the last 72 hours). After fitting the model, we will investigate the validity of the assumption of normality. Alternative methods of analyses will be considered if the distribution of the primary effectiveness outcome is non-normal. In this trial, participants may die before antibiotic therapy is discontinued. In such cases the outcome is undefined and is referred to as 'truncated by death'. A crude comparison between the survivors on each treatment arm may give rise to biased outcome comparisons. Therefore, we will consider undertaking some sensitivity analyses to estimate treatment effect having account for the deaths. This will explore different approaches to analysis of ICU trials, that allow incorporation of multiple relevant outcomes, including death, into a single overall measure (e.g., the win ratio⁸, global ranking score⁹, and weighted composite outcome¹⁰).

The primary safety outcome (28-day all-cause mortality) is based on assessing non-inferiority and we specify the null hypothesis that the biomarker interventions are much worse compared with standard-of-care. The primary safety outcome will be analysed using mixed effect logistic regression models, using the same adjustments variables as the primary effectiveness analysis. We will derive risk difference from the fitted logistic regression model to compare the non-inferiority margin for the safety outcome. The unadjusted and adjusted estimates and the 95% confidence intervals will be compared with the non-inferiority margin to accept/reject the null hypothesis. Therefore, our primary effectiveness outcome (antibiotic duration) will not provide all the information as regards the treatment effect. Safety (28-day all-cause mortality) is paramount - only if an intervention arm is not worse than the control (standard care only) will it be acceptable.

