Secondary outcomes will be assessed using an ITT approach. Continuous secondary outcomes will be analysed in the same way to the primary outcome and the categorical outcomes will be assessed using mixed effects logistic regression models. Time-to-event outcomes will be analysed using Cox

proportional hazards models. For all analyses, the adjusted effect estimates will be presented along with their associated 95% confidence interval (CI). In addition, the primary outcomes will also be analysed using Bayesian method as secondary analysis considering both non-informative and informative priors.

Exploratory sub-group analyses for primary effectiveness outcome will be reported using 99% confidence intervals. Linear mixed effect regression will be used with interaction terms (treatment group by sub-group) to estimate sub-group effects. The following sub-groups selected from a recent report about the management of infection causing sepsis in the NHS will be explored:

- Community-acquired pneumonia (CAP)
- Hospital-acquired pneumonia (HAP)
- Urinary tract infection (UTI)
- Intra-abdominal infection
- Infection with positive blood culture

In addition, community acquired, hospital acquired infections and SARS-COV-2 will be analysed as subgroup. Moreover, we will do the following subgroups analysis

- Sepsis vs Septic Shock
- Ward vs ICU where the intervention was stopped
- Surgery vs non-surgery on previous 72 hours

An exploratory analysis will be done to investigate weekend effect on the primary effectiveness outcome, the total duration of antibiotic treatment to 28 days from randomisation. Monitoring of the protocol processes and compliance measures is important in this trial (as detailed in section 4). These measures will be monitored and reported to the DMC throughout the trial. A final summary of the protocol processes and compliance will be presented at the end of the trial.

Handling missing data

Every effort will be made to minimise missing data both in baseline and outcome in the trial. Missing data will be assessed carefully. For the primary outcome (duration of antibiotics), start and stop dates for each course of antibiotics are required in order to compute the total duration for each participant. There will be no missing for start dates as the start dates and times will be the

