	Missing	xx.xx	xx.xx	xx.xx	xx.xx
Time from first research blood sample taken for the trial to first research blood sample delivered					
	N	xx.xx	xx.xx	xx.xx	xx.xx
	Mean (SD)	xx.xx	xx.xx	xx.xx	xx.xx
	Median (IQR)	xx.xx	xx.xx	xx.xx	xx.xx
	Missing	xx.xx	xx.xx	xx.xx	xx.xx

SECTION 3 - PARTICIPANT FOLLOW-UP

Table 8: Follow-up rates throughout the trial

Treatment Group	Time-point	Total to reach time point	Completed	Withdrawn completely	Deceased	Incomplete data
Standard Care	Baseline	N	n (%)	n (%)	n (%)	n (%)
	28 days	N	n (%)	n (%)	n (%)	n (%)
	90 days	N	n (%)	n (%)	n (%)	n (%)
PCT	Baseline	N	n (%)	n (%)	n (%)	n (%)
	28 days	N	n (%)	n (%)	n (%)	n (%)
	90 days	N	n (%)	n (%)	n (%)	n (%)
CRP	Baseline	N	n (%)	n (%)	n (%)	n (%)
	28 days	N	n (%)	n (%)	n (%)	n (%)
	90 days	N	n (%)	n (%)	n (%)	n (%)

Table 9: Overall summary of withdrawals by treatment arm*

Withdrawal decision	Withdrawn from intervention only but remains on follow-up			Withdrawn from intervention completely and will not be followed-up		
	Standard care	PCT	CRP	Standard care	PCT	CRP
Participant's decision						
Consultee's decision						
Clinical team decision						
Antibiotics stopped due to futility						
Determined to require long term antibiotics (>21 days) after randomisation						
Other						

* Summary of total number of withdrawal requests i.e. participants may have more than one request

Table 10: Primary cause of death summarised by treatment arm

	Standard care	PCT	CRP	TOTAL	P-value
Sepsis or sepsis related (including organ/multi-organ failure)	n (%)	n (%)	n (%)	N	
Not related to sepsis	n (%)	n (%)	n (%)	N	

Table 11: Number of participant's withdrawing completely throughout the trial

	Standard care	PCT	CRP	TOTAL	P-value
Post-randomisation to ICU discharge	n (%)	n (%)	n (%)	N	
ICU discharge to Hospital discharge	n (%)	n (%)	n (%)	N	
Hospital discharge to 28 day follow-up	n (%)	n (%)	n (%)	N	
28 day follow-up to 90 day follow-up	n (%)	n (%)	n (%)	N	
Overall	n (%)	n (%)	n (%)	N	

Table 12: Number of deaths throughout the trial

	Standard care	PCT	CRP	TOTAL	P-value
Post-randomisation to ICU discharge	n (%)	n (%)	n (%)	N	
ICU discharge to Hospital discharge	n (%)	n (%)	n (%)	N	
Hospital discharge to 28 day follow-up	n (%)	n (%)	n (%)	N	
28 day follow-up to 90 day follow-up	n (%)	n (%)	n (%)	N	
Overall	n (%)	n (%)	n (%)	N	

Table 13: Time from randomisation to death, withdrawal and follow-up summarised by treatment arm

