	Standard care	PCT	CRP	PCT vs. Standard care Unadjusted mean difference (95% CI); p-value	CRP vs. Standard care Unadjusted mean difference (95% CI); p-value
Time from randomisation to withdrawing completely from trial					
N	xx.xx	xx.xx	xx.xx		
Mean (SD)	xx.xx	xx.xx	xx.xx		
Median (IQR)	xx.xx	xx.xx	xx.xx		
Missing	xx.xx	xx.xx	xx.xx		
Time from randomisation to death					
N	xx.xx	xx.xx	xx.xx		
Mean (SD)	xx.xx	xx.xx	xx.xx		
Median (IQR)	xx.xx	xx.xx	xx.xx		
Missing	xx.xx	xx.xx	xx.xx		
Time from randomisation to 28- day follow-up					
N	xx.xx	xx.xx	xx.xx		
Mean (SD)	xx.xx	xx.xx	xx.xx		
Median (IQR)	xx.xx	xx.xx	xx.xx		
Missing	xx.xx	xx.xx	xx.xx		
Time from randomisation to 90-day follow-up					
N	xx.xx	xx.xx	xx.xx		
Mean (SD)	xx.xx	xx.xx	xx.xx		
Median (IQR)	xx.xx	xx.xx	xx.xx		

Missing	xx.xx	xx.xx	xx.xx		
---------	-------	-------	-------	--	--

SECTION 4 - INTERVENTION DATA

Table 14: Daily data collection – summary of patient status

	Standard care	PCT	CRP	PCT vs. Standard care Adjusted mean difference (95% CI)	CRP vs. Standard care Adjusted mean difference (95% CI)
Number of days as hospital inpatient					
N	xx.xx	xx.xx	xx.xx		
Mean (SD)	xx.xx	xx.xx	xx.xx		
Median (IQR)	xx.xx	xx.xx	xx.xx		
Missing	xx.xx	xx.xx	xx.xx		
Number of days not a critical care inpatient					
N	xx.xx	xx.xx	xx.xx		
Mean (SD)	xx.xx	xx.xx	xx.xx		
Median (IQR)	xx.xx	xx.xx	xx.xx		
Missing	xx.xx	xx.xx	xx.xx		
Number of days in level 3 unit (ICU)					
N	xx.xx	xx.xx	xx.xx		
Mean (SD)	xx.xx	xx.xx	xx.xx		
Median (IQR)	xx.xx	xx.xx	xx.xx		
Missing	xx.xx	xx.xx	xx.xx		
Number of days level 2 unit (HDU)					
N	xx.xx	xx.xx	xx.xx		
Mean (SD)	xx.xx	xx.xx	xx.xx		
Median (IQR)	xx.xx	xx.xx	xx.xx		
Missing	xx.xx	xx.xx	xx.xx		
Number of days deemed fit for hospital discharge by treating clinical team					
N	xx.xx	xx.xx	xx.xx		
Mean (SD)	xx.xx	xx.xx	xx.xx		
Median (IQR)	xx.xx	xx.xx	xx.xx		
Missing	xx.xx	xx.xx	xx.xx		

Table 15: Summary of blood sampling process by treatment arm

	Standard care	PCT	CRP	Total	PCT vs. Standard care Adjusted estimate (95% CI)	CRP vs. Standard care Adjusted estimate (95% CI)
Duration from the time blood sample taken to the time blood analysis starts (minutes)						
N	xx.xx	xx.xx	xx.xx	xx.xx		
Mean (SD)	xx.xx	xx.xx	xx.xx	xx.xx		
Median (IQR)	xx.xx	xx.xx	xx.xx	xx.xx		
Missing	xx.xx	xx.xx	xx.xx	xx.xx		
Time taken to analyse blood sample (minutes)						
N	xx.xx	xx.xx	xx.xx	xx.xx		
Mean (SD)	xx.xx	xx.xx	xx.xx	xx.xx		
Median (IQR)	xx.xx	xx.xx	xx.xx	xx.xx		

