Table 21: Summary of total duration of antibiotic treatment from randomisation to 28 days by treatment group (Primary outcome)

	Standard care	PCT	CRP	PCT vs. Standard care Adjusted mean difference (95% CI)	CRP vs. Standard care Adjusted mean difference (95% CI)
Duration of antibiotic treatment to 28 days (days)					
N	xx.xx	xx.xx	xx.xx		
Mean (SD)	xx.xx	xx.xx	xx.xx		
Median (IQR)	xx.xx	xx.xx	xx.xx		
Missing	xx.xx	xx.xx	xx.xx		

Primary safety outcome

Table 22: Summary of 28-day all-cause mortality by treatment group (Primary outcome)

	Standard care	PCT	CRP	PCT vs. Standard care Adjusted OR (95% CI)	CRP vs. Standard care Adjusted OR (95% CI)
Mortality status 28 days post randomisation					
Dead	n (%)	n (%)	n (%)		
Alive	n (%)	n (%)	n (%)		
Missing	n (%)	n (%)	n (%)		

Secondary effectiveness and safety outcomes to 28 days

Table 23: Summary of secondary effectiveness and safety outcomes by treatment group

	Standard care	PCT	CRP	PCT vs. Standard care Adjusted estimate (95% CI)	CRP vs. Standard care Adjusted estimate (95% CI)
Mortality status 90 days post randomisation					
Dead	n (%)	n (%)	n (%)		
Alive	n (%)	n (%)	n (%)		
Missing	n (%)	n (%)	n (%)		
Antibiotic dose (Daily Defined Dose)					
N	xx.xx	xx.xx	xx.xx		
Mean (SD)	xx.xx	xx.xx	xx.xx		
Median (IQR)	xx.xx	xx.xx	xx.xx		
Missing	xx.xx	xx.xx	xx.xx		
Patient required unscheduled care escalation					
No	n (%)	n (%)	n (%)		
Yes	n (%)	n (%)	n (%)		
Missing	n (%)	n (%)	n (%)		
Number of unscheduled care escalations					
1	n (%)	n (%)	n (%)		

	2	n (%)	n (%)	n (%)		
	...	n (%)	n (%)	n (%)		
	Total	n	n	n		
	Missing	n (%)	n (%)	n (%)		
Patient had infection relapse/recurrence requiring further antibiotic treatment						
	No	n (%)	n (%)	n (%)		
	Yes	n (%)	n (%)	n (%)		
	Missing	n (%)	n (%)	n (%)		
Number of infection relapses/recurrences						
	1	n (%)	n (%)	n (%)		
	2	n (%)	n (%)	n (%)		
	...	n (%)	n (%)	n (%)		
	Total	n	n	n		
	Missing	n (%)	n (%)	n (%)		
Number of super-infections defined as new infection at a different anatomical site						
	1	n (%)	n (%)	n (%)		
	2	n (%)	n (%)	n (%)		
	...	n (%)	n (%)	n (%)		
	Total	n	n	n		
	Missing	n (%)	n (%)	n (%)		
Time from randomisation to first 'fit' for hospital discharge						
	N	xx.xx	xx.xx	xx.xx		
	Mean (SD)	xx.xx	xx.xx	xx.xx		
	Median (IQR)	xx.xx	xx.xx	xx.xx		
	Missing	xx.xx	xx.xx	xx.xx		

Subgroup analyses

Table 24: Sub-group analyses on the duration of antibiotic days from randomisation to day 28

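### Table 13 tests mean time to death and to withdrawal only among those who had the event, so these entries are not randomised comparisons and should be removed

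*SAP*

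**What the plan says.** Table 13, in Section 3 (Participant follow-up) of the template tables, is titled "Time from randomisation to death, withdrawal and follow-up summarised by treatment arm". Its rows include "Time from randomisation to death" and the time to complete withdrawal from the trial. Each row has N, mean (SD), median (IQR) and missing. The comparison columns are headed "PCT vs. Standard care Unadjusted mean difference (95% CI); p-value", with a matching column for CRP. The same headings cover the rows for time to the 28-day and 90-day follow-ups.

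The Analysis methods section discusses death as a problem for antibiotic duration only: "In such cases the outcome is undefined and is referred to as 'truncated by death". It adds that "A crude comparison between the survivors on each treatment arm may give rise to biased outcome comparisons".

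A smaller, related point concerns the secondary outcome "Time to 'fit' for hospital discharge". In the paragraph on secondary outcomes the SAP says "Time-to-event outcomes will be analysed using Cox" proportional hazards models, without a rule for participants who die first. Table 23 lays out "Time from randomisation to first 'fit' for hospital discharge" as N, mean (SD), median (IQR) and missing, with an adjusted-estimate column for each biomarker arm.

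**The concern.** A time to death is recorded only for someone who died. Comparing its mean between arms compares two groups formed after randomisation by the outcome itself. If a biomarker arm has extra deaths, those deaths join its group and move its mean in whichever direction their timing dictates. The result can favour the arm with more deaths, count against it, or show nothing. The time-to-withdrawal row has the same structure.

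The SAP already warns that comparing survivors alone may be biased. Comparing only the dead has the same fault, yet here it comes with a confidence interval and a p-value. A pre-specified p-value on time to death, in a trial where safety is a primary question, invites a reading that it cannot support.

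**Working it through.** The SAP gives no figure for this comparison, so there is none to reproduce. The check asks what the planned statistic would show when mortality truly differs.

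**Inputs from the SAP (Sample size, Trial design).** Total 2760, allocated 1:1:1; 28-day mortality 15%; margin 5.4 percentage points; withdrawal 5%.

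**Assumptions, not from the SAP.** Deaths are followed to day 28. In the control arm half the deaths fall uniformly in days 0–7 (mean 3.5) and half uniformly in days 7–28 (mean 17.5).

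1. **Who is compared.** 2760 / 3 = 920 per arm. 0.15 × 920 = 138 deaths, so about 85% of the arm is left out. If the 5% withdrawal allowance were all complete withdrawals, that row would hold 0.05 × 920 = 46 per arm.

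2. **Control mean.** (7.5 × 3.5 + 7.5 × 17.5) / 15 = 10.50 days.

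3. **Biomarker arm with 20.4% mortality (15% + 5.4 points).**
   - All excess late: (7.5 × 3.5 + 12.9 × 17.5) / 20.4 = 12.35 days, difference +1.85.
   - Excess proportional: (10.2 × 3.5 + 10.2 × 17.5) / 20.4 = 10.50 days, difference 0.
   - All excess early: (12.9 × 3.5 + 7.5 × 17.5) / 20.4 = 8.65 days, difference −1.85.

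4. **Biomarker arm with a 3-point excess, all late.** (7.5 × 3.5 + 10.5 × 17.5) / 18 = 11.67 days, difference +1.17.

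5. **How often the test would favour the worse arm.** Simulation used 920 × 0.95 = 874 evaluable per arm, 4000 runs and a two-sample t-test.

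| Excess deaths | Mean difference (days) | p < 0.05 in favour of the worse arm |
|---|---|---|
| 5.4 points, late | +1.84 | 47% |
| 3 points, late | +1.18 | 22% |
| 5.4 points, proportional | about 0 | 2.5% |
| 5.4 points, early | −1.87 | 0% |

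The simulated differences agree with steps 3 and 4. The 2.5% in the proportional case is what chance alone gives in one tail.

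6. **Contrast with an analysis of everyone.** Under a constant hazard to day 28, mortality of 15% versus 20.4% gives a hazard ratio of ln(1 − 0.204) / ln(1 − 0.15) = 1.40. The mean time to death among the dead is 13.62 versus 13.47 days, a difference of −0.15. The all-participant analysis shows the harm and the Table 13 statistic hardly registers it.

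7. **Time to 'fit' for discharge.** Assume 35% of patients are slow to recover (mean 20 days, against 8 for the rest), deaths occur only among them, death times are uniform over 28 days, and mortality is 15% versus 20.4%.
   - Mean time among those who became fit: 7.83 versus 7.64 days.
   - Death-censored rate ratio: 1.02.
   - Fit by day 28, with deaths counted as never fit: 85.1% versus 83.5%.
   - With 874 per arm there are about 743 and 730 events. The standard error of the log ratio is √(1/743 + 1/730) = 0.052, so the 95% interval is about 0.92 to 1.13.

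   The higher-mortality arm looks marginally faster while fewer of its patients become fit, but the effect is far too small to be read as benefit.

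**The case against.** The strongest reply is that Table 13 is a follow-up description and not an outcome table. It sits in Section 3, its column headings also serve the follow-up timing rows, and no decision rule uses it. Excess deaths would be visible against full denominators in Table 8 (deceased), Table 12 (deaths by period and overall, with a p-value, immediately before Table 13), Table 22 (28-day mortality) and Table 23 (90-day mortality). This stands and limits the reach of the point. It does not justify printing a confidence interval and p-value for a comparison with no sound interpretation.

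Three stronger readings are tempting, and the SAP does not support them.

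- **That Table 13 contradicts the Cox sentence.** A reader might infer this. But that sentence belongs to the paragraph on secondary outcomes, and time to death is not a listed outcome. Mortality is defined as status at day 28 and at 90 days, and the 28-day primary is analysed by mixed-effects logistic regression with a derived risk difference.
- **That the table makes the deadlier arm look safer.** It does so only when the extra deaths come late. With early excess the sign reverses, and with proportional excess there is nothing to see.
- **That time to 'fit' is analysed wrongly.** The SAP does not say that deaths are censored. A Cox model that censors at death estimates a cause-specific hazard, which is legitimate if declared, and Table 23's adjusted-estimate column can hold a hazard ratio. What remains is an undeclared convention with a small effect.

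**Conclusion.** The point holds for the death and withdrawal rows of Table 13. Their planned mean differences, intervals and p-values rest on subsets defined by the event, about 138 of 920 per arm for death at 15% mortality. For a true excess equal to the margin, the difference in mean time to death ran from about −1.9 to +1.8 days on timing alone. In the late-excess case it reached p < 0.05 in favour of the worse arm in 47% of runs. Those sizes depend on the assumed timings. That the comparison is not a randomised one does not depend on them. No numerical case was worked for withdrawal, where the argument is structural.

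Neither the non-inferiority conclusion nor any other primary result is at stake. The missing rule for deaths in time to 'fit' is a minor addition.

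**What to change.** In Table 13, remove the mean-difference and p-value entries for the death and complete-withdrawal rows. Keep their descriptive summaries, and leave the 28-day and 90-day follow-up timing rows as they are. If a between-arm comparison of time to death is wanted, give Kaplan-Meier curves with a Cox hazard ratio on all randomised participants.

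As a minor addition, state in Analysis methods how deaths are handled for time to 'fit' for discharge. In Table 23, show the cumulative incidence of becoming fit by day 28, with deaths counted as never fit, beside the Cox result.

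The cost is an edit to two table shells, one or two sentences of text and a few lines of code. No new data should be needed, since the planned tables already use the time to death and the time to first 'fit'. The downside is one extra estimate to explain.

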randomisation dates and times. In the event that stop dates are unobtainable and thus missing, we will first look to see if the participant either withdrew completely or died. If so, we will use the withdrawal/death date as the stop date to estimate the duration for a particular course of antibiotics. If they did not withdraw or die, then we would impute the duration for that particular course of antibiotics using the mean duration of all antibiotics for the participant.

The SOFA score is to be collected baseline at day 3 and day 7, however, date may not be available on these particular days hence this score would be missing. In this situation, we'll use the value from the day before. If this is not available, then we'll use the value of the day after. If neither are available, then the value for that particular day will be missing.

Additional analyses

The primary analysis looks at the total duration of antibiotic days from randomisation to day 28. However, it is also of interest to assess the duration of antibiotics during the intervention phase only i.e., when the biomarker guidance is in use, and also from randomisation to ICU discharge. Therefore, additional analyses will estimate the treatment effect for the duration of antibiotic days during the intervention phase only and also to the point of ICU discharge. Similarly, we will also estimate the same treatment effects for the daily defined dose (DDD) secondary outcome.

The impact of COVID-19 pandemic on the trial will be assessed on completion of the trial. The baseline demographics and primary outcomes for participants recruited before COVID-19 will be compared to those recruited during COVID-19. The objective is to assess if there is any change in the population considered for the trial. In addition, for participants recruited during the COVID-19 pandemic period, baseline demographics and primary outcomes will be compared for COVID positive versus COVID negative participants. We also perform a sensitivity analysis by dropping COVID positive participants to see if COVID pandemic has an impact on the trial. We will do a sensitivity analysis to account for the non-compliant sites with PCT testing during intervention and follow-up phase. The plan is to run the primary outcome analysis excluding the non-compliant sites and see if any difference between the arms.

Safety

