Was intravenous crystalloid fluid administered for hypotension or raised lactate level					
	No	n (%)	n (%)	n (%)	n (%)
	Yes	n (%)	n (%)	n (%)	n (%)
	Missing	n (%)	n (%)	n (%)	n (%)
Were broad spectrum antibiotics administered					
	No	n (%)	n (%)	n (%)	n (%)
	Yes	n (%)	n (%)	n (%)	n (%)
	Missing	n (%)	n (%)	n (%)	n (%)
Was anti-fungal treatment used as part of the 3-hour treatment bundle					
	No	n (%)	n (%)	n (%)	n (%)
	Yes	n (%)	n (%)	n (%)	n (%)
	Missing	n (%)	n (%)	n (%)	n (%)
Was anti-viral treatment used as part of the 3-hour treatment bundle					
	No	n (%)	n (%)	n (%)	n (%)
	Yes	n (%)	n (%)	n (%)	n (%)
	Missing	n (%)	n (%)	n (%)	n (%)
Within 12 hours of presentation					
Source control (e.g. surgical/radiological abscess drainage, vascular line removal)					
	No	n (%)	n (%)	n (%)	n (%)
	Yes	n (%)	n (%)	n (%)	n (%)
	Missing	n (%)	n (%)	n (%)	n (%)
Within 24 hours of presentation					
Was the patient started on systemic steroids (IV or oral)					
	No	n (%)	n (%)	n (%)	n (%)
	Yes	n (%)	n (%)	n (%)	n (%)
	Missing	n (%)	n (%)	n (%)	n (%)

Was the patient put on renal replacement therapy				
	No	n (%)	n (%)	n (%)
	Yes	n (%)	n (%)	n (%)
	Missing	n (%)	n (%)	n (%)

Table 6: Baseline outcome measures

		Standard care	PCT	CRP	TOTAL
qSOFA	N	xx.xx	xx.xx	xx.xx	xx.xx
	Mean (SD)	xx.xx	xx.xx	xx.xx	xx.xx
	Median (IQR)	xx.xx	xx.xx	xx.xx	xx.xx
	Missing	xx.xx	xx.xx	xx.xx	xx.xx
SOFA	N	xx.xx	xx.xx	xx.xx	xx.xx
	Mean (SD)	xx.xx	xx.xx	xx.xx	xx.xx
	Median (IQR)	xx.xx	xx.xx	xx.xx	xx.xx
	Missing	xx.xx	xx.xx	xx.xx	xx.xx
APACHE II	N	xx.xx	xx.xx	xx.xx	xx.xx
	Mean (SD)	xx.xx	xx.xx	xx.xx	xx.xx
	Median (IQR)	xx.xx	xx.xx	xx.xx	xx.xx
	Missing	xx.xx	xx.xx	xx.xx	xx.xx

Table 7: Summary of process data at baseline summarised by treatment arm

		Standard care	PCT	CRP	TOTAL
Time from consent to randomisation (mins)	N	xx.xx	xx.xx	xx.xx	xx.xx
	Mean (SD)	xx.xx	xx.xx	xx.xx	xx.xx
	Median (IQR)	xx.xx	xx.xx	xx.xx	xx.xx
	Missing	xx.xx	xx.xx	xx.xx	xx.xx
Time from hospital admission to randomisation (mins)	N	xx.xx	xx.xx	xx.xx	xx.xx
	Mean (SD)	xx.xx	xx.xx	xx.xx	xx.xx
	Median (IQR)	xx.xx	xx.xx	xx.xx	xx.xx
	Missing	xx.xx	xx.xx	xx.xx	xx.xx
Time from ICU/HDU admission to randomisation					

	N	xx.xx	xx.xx	xx.xx	xx.xx
	Mean (SD)	xx.xx	xx.xx	xx.xx	xx.xx
	Median (IQR)	xx.xx	xx.xx	xx.xx	xx.xx
	Missing	xx.xx	xx.xx	xx.xx	xx.xx
Time from randomisation to first research blood sample taken for the trial					
	N	xx.xx	xx.xx	xx.xx	xx.xx
	Mean (SD)	xx.xx	xx.xx	xx.xx	xx.xx
	Median (IQR)	xx.xx	xx.xx	xx.xx	xx.xx

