	Standard care	PCT	CRP	Total	PCT vs. Standard care Adjusted estimate (95% CI)	CRP vs. Standard care Adjusted estimate (95% CI)
Participant discharged alive from treating hospital						
No	n (%)	n (%)	n (%)	n (%)		
Yes	n (%)	n (%)	n (%)	n (%)		
Missing	n (%)	n (%)	n (%)	n (%)		
Discharge location						
Home	n (%)	n (%)	n (%)	n (%)		
Another hospital	n (%)	n (%)	n (%)	n (%)		
Nursing/residential home						
Other	n (%)	n (%)	n (%)	n (%)		
Missing	n (%)	n (%)	n (%)	n (%)		
Participant discharged on a course of systemic (IV/oral/rectal) antibiotics						
No	n (%)	n (%)	n (%)	n (%)		
Yes	n (%)	n (%)	n (%)	n (%)		
Missing	n (%)	n (%)	n (%)	n (%)		
Time from randomisation to discharge						
N	xx.xx	xx.xx	xx.xx	xx.xx		
Mean (SD)	xx.xx	xx.xx	xx.xx	xx.xx		

Median (IQR)	xx.xx	xx.xx	xx.xx	xx.xx	
Missing	xx.xx	xx.xx	xx.xx	xx.xx	

Table 19: Summary of readmission data by treatment arm

	Standard care	PCT	CRP	Total	PCT vs. Standard care Adjusted estimate (95% CI)	CRP vs. Standard care Adjusted estimate (95% CI)
Participant unscheduled readmission						
No	n (%)	n (%)	n (%)	n (%)		
Yes	n (%)	n (%)	n (%)	n (%)		
Missing	n (%)	n (%)	n (%)	n (%)		
Participant readmission to						
Same hospital	n (%)	n (%)	n (%)	n (%)		
Different hospital	n (%)	n (%)	n (%)	n (%)		
Missing	n (%)	n (%)	n (%)	n (%)		
Participant readmitted from						
Home	n (%)	n (%)	n (%)	n (%)		
Another hospital	n (%)	n (%)	n (%)	n (%)		
Nursing/residential home	n (%)	n (%)	n (%)	n (%)		
Other	n (%)	n (%)	n (%)	n (%)		
Missing	n (%)	n (%)	n (%)	n (%)		
Participant required antibiotics as part of reason for readmission or prior to readmission						
No	n (%)	n (%)	n (%)	n (%)		
Yes	n (%)	n (%)	n (%)	n (%)		
Missing	n (%)	n (%)	n (%)	n (%)		
Time from discharge to readmission						
N	xx.xx	xx.xx	xx.xx	xx.xx		
Mean (SD)	xx.xx	xx.xx	xx.xx	xx.xx		
Median (IQR)	xx.xx	xx.xx	xx.xx	xx.xx		
Missing	xx.xx	xx.xx	xx.xx	xx.xx		

SECTION 5 - STUDY OUTCOME DATA

Table 20: Summary of day 3 and day 7 SOFA score by treatment arm

	Standard care	PCT	CRP	PCT vs. Standard care Adjusted mean difference (95% CI)	CRP vs. Standard care Adjusted mean difference (95% CI)
Day 3 SOFA score					
N	xx.xx	xx.xx	xx.xx		
Mean (SD)	xx.xx	xx.xx	xx.xx		
Median (IQR)	xx.xx	xx.xx	xx.xx		
Missing	xx.xx	xx.xx	xx.xx		
Day 7 SOFA score					
N	xx.xx	xx.xx	xx.xx		
Mean (SD)	xx.xx	xx.xx	xx.xx		
Median (IQR)	xx.xx	xx.xx	xx.xx		
Missing	xx.xx	xx.xx	xx.xx		

Primary effectiveness outcome

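### The day-3 and day-7 SOFA contrasts in SAP Table 20 name no covariates, and the SAP's only adjustment set omits baseline SOFA, which costs some precision in a supporting outcome

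*SAP*

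**What the plan says.** The template table "Table 20: Summary of day 3 and day 7 SOFA score by treatment arm", in the section on study outcome data, compares SOFA between arms at both days. Its contrast columns are headed "PCT vs. Standard care Adjusted mean difference (95% CI"), with a matching column for CRP. Neither the table nor a footnote lists covariates.

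The only adjustment set in the SAP is under Analysis methods, for the primary effectiveness outcome: the model is fitted "having adjusted for age, gender and the stratification variables (sepsis severity, recruiting centre (random effect) and surgery within the last 72 hours"). The same section extends that model: "Continuous secondary outcomes will be analysed in the same way to the primary outcome". It also says "For all analyses, the adjusted effect estimates will be presented along with their associated 95% confidence interval (CI"). No outcome-specific baseline value is added anywhere.

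Baseline SOFA is available. Handling missing data says "The SOFA score is to be collected baseline at day 3 and day 7". Baseline patient characteristics lists it, and "Table 6: Baseline outcome measures" summarises it for every arm. No section uses it as a covariate.

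Day-3 and day-7 SOFA appears in neither list of secondary outcomes (Primary and secondary outcomes; Outcome definitions).

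**The concern.** A covariate set written for antibiotic duration has been carried to an outcome of a different kind. Antibiotic duration after randomisation, dose and mortality have no baseline measurement of themselves; SOFA has one. When an outcome is a repeat of a graded score taken a few days earlier, the earlier score would normally be expected to explain part of its variance. The only severity term in the planned set is the two-level factor sepsis or septic shock, which cannot carry all the information in the score.

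Leaving baseline SOFA out makes the intervals in Table 20 wider than the data require. Because the table does not define its adjustment, adding the covariate after the results are known could look data-driven.

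**Working it through.** **No figure in the plan to reproduce.** The SAP gives no SD, effect size, power or baseline-to-follow-up correlation for SOFA. The correlation is therefore an assumption and is shown over a range.

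**Formulas.** Let r be the partial correlation of baseline SOFA with day-3 or day-7 SOFA, given the planned covariates. Adding baseline SOFA multiplies the residual variance by 1 − r² and the CI width by √(1 − r²). The gain equals multiplying the number of participants by 1/(1 − r²).

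| r (assumed) | 1 − r² | √(1 − r²) | CI narrower by | Equivalent extra participants |
|---|---|---|---|---|
| 0.3 | 0.91 | 0.954 | 4.6% | 9.9% |
| 0.4 | 0.84 | 0.917 | 8.3% | 19% |
| 0.5 | 0.75 | 0.866 | 13.4% | 33% |
| 0.6 | 0.64 | 0.800 | 20.0% | 56% |

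**Absolute scale.** Inputs from the SAP (Trial design; Sample size): 2760 participants, allocation 1:1:1, 5% withdrawal. That gives 2760/3 = 920 per arm and 920 × 0.95 = 874 analysed. This is an upper bound for SOFA, since some participants will have died or left hospital. In units of the residual SD, the 95% half-width for one contrast is:

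- without baseline SOFA: 1.96 × √(2/874) = 0.094
- r = 0.3: 0.094 × 0.954 = 0.089
- r = 0.5: 0.094 × 0.866 = 0.081
- r = 0.6: 0.094 × 0.800 = 0.075

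The percentage narrowing does not depend on the number analysed.

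**Overlap with septic shock and the other covariates.** A partial correlation already allows for this overlap. The same allowance can be shown from total explained variance. Suppose, as an assumption, that the planned covariates explain 10% of the variance in later SOFA and the full set with baseline SOFA explains 25% (a multiple correlation of 0.5). The variance ratio is 0.75/0.90 = 0.833 and the CI narrows by 1 − √0.833 = 8.7%. If the planned covariates already explain 20%, the ratio is 0.75/0.80 = 0.938 and the narrowing is 3.2%. The gain is therefore small if the existing covariates carry most of baseline severity.

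**The fill rule.** Handling missing data replaces a missing SOFA with the previous day's value or, failing that, the next day's. The sentence introducing the rule names baseline together with days 3 and 7. Read literally, a missing baseline score could be filled from the day after, which may be after randomisation. Such a value should not enter the model as a baseline covariate, so the rule has to be limited when the covariate is added.

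**The case against.** The strongest reply is that the omission is inferred. Table 20 lists no covariates, and the rule that extends the primary model speaks of secondary outcomes, a group to which day-3 and day-7 SOFA does not formally belong. A strict reader could say that the SOFA model is unspecified, not that it excludes baseline SOFA. That is fair as a limit on certainty, but the remedy is the same: the SAP has only one meaning of adjusted to offer, and it does not include baseline SOFA.

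The second reply is that little is lost. The half-width is already about 0.094 SD at the upper-bound sample size, the range for r is assumed, and the association may weaken between day 3 and day 7. A common covariate set is also a valid choice. All of this stands, and it makes the point an efficiency gain rather than an error.

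Three stronger readings are tempting, and the SAP does not support them.

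- A reader might infer that the contrasts are unadjusted. They are adjusted, but apparently for a set without baseline SOFA.
- A reader might infer that chance imbalance in baseline SOFA biases the estimates. Allocation is random, with minimisation on sepsis severity, and that factor is in the model. Any remaining imbalance is chance variation, which the interval already allows for.
- A reader might infer that the safety claim is weakened. The SAP rests safety on 28-day all-cause mortality with a non-inferiority margin. It gives SOFA no hypothesis, margin or decision rule and nowhere links it to that claim.

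**Conclusion.** The point holds as a modest loss of precision. As written, the only adjustment that can be applied to Table 20 leaves out a baseline value that the trial already collects. For partial correlations of 0.3 to 0.6, including it would narrow the 95% intervals by about 5% to 20%. The gain would be smaller if the planned covariates already account for most of baseline severity. The conclusion rests on two things: reading the adjustment in Table 20 as the set under Analysis methods, and an assumed correlation that the SAP does not give. It concerns a supporting outcome; it does not bias any estimate and cannot change the conclusion on antibiotic duration or on 28-day mortality.

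**What to change.** Three short additions to the SAP:

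1. In Analysis methods and in a Table 20 footnote, state that the day-3 and day-7 SOFA models add baseline SOFA as a continuous fixed covariate to the existing adjustment set, using pre-randomisation values only.
2. In Handling missing data, state that filling from the following day does not apply to the baseline value.
3. State that a missing baseline SOFA is handled by mean imputation with a missing indicator, so that no participant is dropped from the comparison for lack of it.

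The cost is one extra covariate and a rule for missing baseline values; no new data are needed. The change does not deal with SOFA that is undefined after death or unavailable after discharge, which is a separate question about the same table.
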